Like other evidence-based PT programs, PCIT has led to substantial improvements in parent and child outcomes. However, among children with very high rates of behavior problems, researchers have reported the strongest effects with PCIT, with effect sizes ranging from .61 (parent reported child behavior problems) to 5.67 (observed parent behavior) when compared to untreated waiting-list controls. Studies have also shown that most children retain improvements 3 to 6 years post-treatment. Based on the strength of these data, PCIT is considered to be the "gold standard" among individually-delivered PT. It is also one of the most widely disseminated PT programs in the United States, with "PCIT laboratories" for training graduate students and clinicians offered at 8 major universities.

Date: January 30, 2012
Principal Investigator: [name]
Application Number: NA_00039328

Although impressive, these data only reflect outcomes for “completers,” parents who start PCIT and do not drop out before they have completed the program. In a recent study of attrition from PCIT, 36% of parents prematurely stopped attending PCIT and the most common reason cited by parents was “disagreement with the treatment approach.” In addition, like many other PT programs, the strongest predictor of premature termination was low socioeconomic status. These data suggest that PCIT may not be viewed as useful or relevant by many economically disadvantaged parents. In addition, since most PCIT studies include samples that are predominantly non-Latino White, it is unclear how effective this program is among low-income ethnic minority families. Although there have been some efforts to adapt PCIT to other populations, rigorous trials of these adaptations have not been conducted. In sum, like many treatments identified as “gold standards,” its validity for low income, ethnic minority populations has not been sufficiently evaluated.

The Chicago Parent Program: Description, Critique, and Justification. Funded by a grant from the NINR, the Chicago Parent Program (CPP) was developed in 2002 specifically to address the gap in evidence-based PT programs for ethnic minority parents. Created in collaboration with an advisory group of African American and Latino parents, the CPP was designed to improve parenting and reduce child behavior problems using strategies that are culturally and contextually relevant for ethnic minority parents of young children living in low-income urban neighborhoods.

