- f. Definition of treatment failure or participant removal criteria: Participants will be removed from the study if they (a) lose custody of the target child during the course of treatment, (b) attend treatment sessions under the influence of drugs or alcohol, (c) become actively psychotic or aggressive during treatments, or (d) are uncooperative/noncompliant with the baseline research evaluation or with the

Date: January 30, 2012
Principal Investigator: [name]
Application Number: NA_00039328

Time 2 and Time 3 evaluations. Participants who are removed from the study for these reasons will still be eligible to receive all other treatments routinely available to them at the Family Center.

g. Description of what happens to participants receiving therapy when study ends or if participation in the study ends prematurely: Participants will remain eligible to receive all other treatments normally available to them at the Family Center.

5. Inclusion/Exclusion Criteria

Parent Inclusion criteria are (a) “parent” is the biological or adoptive parent or the legal guardian for the target child being treated at the Kennedy Krieger Institute, (b) parent is English- speaking, (c) child is 2-5 years old, (d) child is brought to the Family Center by the parent/legal guardian because of externalizing or internalizing behavior problems, and (e) willing to be randomly assigned to PCIT or CPP. There will also be 13 clinicians participating in this study and we expect all of them to be female.

Therapist inclusion criteria are (1) employed by the Family Center, (2) graduate-prepared licensed social worker, psychologist, professional counselor or equivalent, and (3) completed necessary training to provide PCIT or CPP

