Application Number: NA_00039328

standard deviations. We will use the more conservative two-sided test. Thus, with 300 participants (150/condition) we will have 99% power to detect this difference using a two-sample comparison of means with alpha=0.05.

Hypothesis testing will mainly be conducted using repeated-measures MANOVA. Should the MANOVA be significant, univariate ANOVA will follow to identify the source of those differences. MANOVA was determined to be a more desirable approach than random regression models because MANOVA corrects for multiple tests of hypotheses. All baseline difference analyses and hypothesis testing will be conducted using 2-tailed tests and alpha =.05 (except tests to examine baseline differences between conditions, which will use .01 to correct for the multiple tests of hypotheses).

d. Early stoppage rules. Interventions will be discontinued if (a) more than 50% of parent participants in either condition report dissatisfaction on consumer satisfaction surveys with their assigned intervention or (b) more than 50% of child participants' CBCL scores (in either condition) worsen from baseline by $> .5$ SD. In this event, the research team will immediately convene with the members of the DSM committee to carefully review the protocol, reasons for dissatisfaction, and recommendations for change. A data safety and monitoring committee will meet early in the first year of the study to make additional recommendations for stoppage rules.

8. Risks

- a. Medical risks. Parent-Child Interaction Therapy and the Chicago Parent Program are psychosocial parent training interventions that have shown no evidence of medical risk. The major risks of this study are disclosure of confidential information and discomfort with the personal nature of some of the survey questions. These risks are no greater than what parents would be exposed to in a mental health treatment setting.
- b. Efforts to minimize risk. Efforts have been taken to minimize risk through appropriate training of research and clinical staff and the use of random number subject identifiers. All therapists have licensed and experienced therapists and have completed the appropriate training (PCIT or CPP).

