- c. Plan for reporting unanticipated problems/study deviations. A Data, Safety, and Monitoring Plan will be comprised of 6 members who will monitor (a) the conduct of the study, (b) recruitment/retention rates, (c) participant satisfaction, (d) the safety of participants, and (e) the validity and integrity of the data. The committee will include the PI ([name]) and the Co-PI ([name]) and four additional members who are not members of the research team: an experienced child psychiatrist, a biostatistician, a clinical trial expert, and a community member. If an adverse event occurs, the event will be reported within 48 hours to the Johns Hopkins University School of Medicine IRB and the NIH Project Officer using the JHU IRB Protocol Event Report with supporting documentation.
- d. Confidentiality: The parent/child participants are all patients of the Family Center and will be provided with the same confidentiality afforded to all patients receiving care at the Family Center at Kennedy Krieger Institute. We will also apply for a Certificate of Confidentiality. Clinicians will not be required to provide personal information as a part of this study.
- e. Financial risks to the participants: Parent training is considered routine care and will be billed to the child's insurance. Childcare will be paid by a grant. There is no financial risk associated with parents' participation in this study.

9. Benefits

Date: January 30, 2012
Principal Investigator: [name]
Application Number: NA_00039328

All participants will receive treatment and both PT treatments offered in this study have been shown to be effective for improving parenting behavior and reducing behavior problems in young children. The potential benefits include: (1) improved child behavior, (2) parent use of more positive child management strategies, (3) improved quality of parent-child relationships, and (4) increased parenting self-efficacy. Since parents in the study will be able to access additional treatments as needed, it can be expected that parents and children who participate in this study will experience improved mental health and wellbeing. Therapists will receive confidential support and supervision for their work with the families.

10. Payment and Remuneration.

Parents who participate in this study will receive the following:

- \$30 gift cards for each fully completed set of assessments (\$90 total for all 3 assessment phases)

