- A book for the target child after each completed assessment phase (value approximately \$5)
- If participants complete all 3 assessment phases, they will also receive a free copy of their video-recorded parent-child play sessions (collected as part of the assessment battery)
- Free childcare at the Family Center for children not involved in the study treatment sessions during the time their parent is attending the study treatment.
- If parent groups are scheduled during the dinner hour (between 5:30 and 8pm), parents and children in the CPP condition will receive free dinner during the study treatment sessions
- Taxi vouchers for participants to and from study treatment sessions

11. Costs

There are no costs associated with participation in this study.

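### Families are removed from the study after assignment and the main test is repeated-measures MANOVA, but no analysis set, rule for removed families' data or missing-data method is stated, so the plan tends to a complete-case comparison

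*Combined protocol and SAP*

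**What the plan says.** Section 4.f states: "Participants will be removed from the study if they" meet any of four criteria. Criterion (a) is loss of custody during treatment. Criteria (b) and (c) are to "attend treatment sessions under the influence of drugs or alcohol, (c) become actively psychotic or aggressive during treatments". Criterion (d) is failure to cooperate with the baseline evaluation or with the "Time 2 and Time 3 evaluations". Sections 4.f and 4.g say only that such families keep access to routine care. Neither mentions their data or further assessment.

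Section 7.c states: "Hypothesis testing will mainly be conducted using repeated-measures MANOVA", with univariate ANOVA to follow. The reason given is that "MANOVA was determined to be a more desirable approach than random regression models because MANOVA corrects for multiple tests of hypotheses". Missing data are not mentioned.

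Three other places touch the subject.
- The Abstract says that data will be collected from all participants at baseline and after the intervention.
- The Background says of the earlier PCIT evidence: "Although impressive, these data only reflect outcomes for" parents who finished the program.
- The Background also calls intent-to-treat the more conservative approach, but about the earlier CPP trial.

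None of these defines an analysis set for this trial.

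**The concern.** Two provisions work together. Criterion (d) turns a missing outcome into removal from the study. The chosen model then, in its standard form, leaves out any family without all of T1, T2 and T3. The model passed over, random regression, would use whatever data a family has. With no stated analysis set and no imputation, the likely default is a comparison of families with complete data. That is the weakness that the protocol points out in earlier PCIT studies.

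The arms compared may then not be the arms randomised. If the lost families differ in child behaviour, and loss or its relation to behaviour differs by arm, the arm difference moves for a reason unrelated to effectiveness. In an equivalence trial such a shift can hide a real difference or, if the programs are equal, make equivalence harder to show.

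Equal loss cannot simply be assumed. Section 4.b gives both programs about 24 hours of treatment, but PCIT as one-hour sessions over 6-8 months and CPP as two-hour sessions over 3 months. Criteria (a) to (c) are tied to treatment or sessions, so exposure to them differs by arm. This says nothing about which arm would lose more.

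**Working it through.** **The plan's own figure.** Section 7.c gives 150 per arm, a margin of 0.5 SD (5 CBCL points, so SD = 10), two-sided alpha 0.05 and 99% power. Power = Φ(0.5/√(2/150) − 1.96) = Φ(4.330 − 1.960) = 0.991, so the figure reproduces. Section 7.c names only a two-sample comparison of means. Two one-sided tests (TOST) at 5% each, with a true difference of 0, give 0.993. The stated power is not in dispute.

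**Cost in numbers (assumed rates).** If 10% of families miss T2 and 10% miss T3, listwise deletion drops:
- 10% if they are the same families (30 of 300)
- 1 − 0.9² = 19% if misses are independent (57)
- 20% if they are different families (60)

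The TOST pass rate for truly equal programs is then 98.6%, 97.5% and 97.3%. Loss of numbers is not the main problem.

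**Selection.** The documents give no assessment-loss rate, so the loss rates p and the correlation ρ between the tendency to be lost and T3 CBCL are assumptions. If a fraction p is lost, the mean of those who remain falls by ρ·c(p) SD, where c(p) = φ(z)/(1 − p) and z = Φ⁻¹(1 − p):
- c(0.05) = 0.1086
- c(0.10) = 0.1950
- c(0.20) = 0.3500

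The shift toward zero is ρ_w·c(p_w) − ρ_b·c(p_b), where w is the truly worse program and b the better one. Example: 0.4 × 0.3500 − 0.4 × 0.1950 = 0.062.

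False equivalence with a true difference of 0.5 SD is close to Φ(shift/SE − 1.645), with SE = √(1/n_w + 1/n_b) and n = 150(1 − p). At 20% v 10%, SE = √(1/120 + 1/135) = 0.1255, and Φ(0.062/0.1255 − 1.645) = 0.125. The t-based calculation agrees.

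| Loss, worse v better | ρ, worse / better | Shift toward zero (SD) | False equivalence |
|---|---|---|---|
| none | n/a | 0 | 5.0% |
| 10% v 5% | 0.2/0.2 to 0.4/0.4 | 0.017 to 0.035 | 6.7 to 8.7% |
| 5% v 10% | 0.2/0.2 to 0.4/0.4 | −0.017 to −0.035 | 3.7 to 2.7% |
| 20% v 10% | 0.2/0.2 to 0.4/0.4 | 0.031 to 0.062 | 8.1 to 12.5% |
| 10% v 20% | 0.2/0.2 to 0.4/0.4 | −0.031 to −0.062 | 2.9 to 1.6% |
| 20% v 10% | 0.4/0.2 | 0.101 | 20.0% |
| 20% v 10% | 0.2/0.4 | −0.008 | 4.4% |
| 20% v 20% | 0.4/0.2 | 0.070 | 13.5% |
| 20% v 20% | 0.2/0.4 | −0.070 | 1.4% |

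Equal loss is harmless only if ρ is also equal in the two arms. If the programs are truly equal, the pass rate at 20% v 10% is 98.0% without a shift, 97.6 to 96.5% with equal ρ, and 93.6% at the 0.101 SD shift.

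**What a mixed model can recover.** If loss depends on T1 or T2 and those data are kept, almost none of the shift remains. If loss depends on T3 itself, roughly 1 − R² of it remains, where R² is from the regression of T3 on T1 and T2. For three equal correlations r, R² = 2r²/(1 + r). That leaves 0.67 of the shift at r = 0.5 and 0.42 at r = 0.7 (assumed values).

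**The case against.** **The harm may be small.** The 8-12% needs a true difference exactly at the margin, twice as much loss in one arm, and that arm to be the worse one. At a true difference of 0.6 SD, the same loss with equal correlations gives about 1-3%. This stands, and it limits the severity.

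**Some text points the other way.** The Abstract speaks of data from all participants, and power is based on all 300. The one is a collection aim and the other a planning number. Neither says who is analysed.

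**Criterion (d) is ambiguous.** The "Time 2 and Time 3 evaluations" could mean noncompliance with either or with both. If both, those families have no post-baseline outcome to analyse, and (d) removes little. This stands. The wording needs settling, and criteria (a) to (c) are unaffected.

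**The investigators considered random regression and gave a reason.** True, but the reason is multiplicity only. Multiple imputation would let MANOVA stay.

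**Stronger readings to resist.** A reader might infer from "gift cards for each fully completed set of assessments" and "If participants complete all 3 assessment phases, they will also receive a free copy" (Section 10) that heavy loss is expected. Such payments are equally a retention measure. A reader might also take the 36% in the Background as a loss rate, but it describes parents who stopped attending PCIT, not missed assessments. Nor do the documents commit to a completers' analysis, or show that loss will differ by arm or favour equivalence. Criterion (d)'s baseline part may also act before assignment.

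**Conclusion.** The point holds as a gap with a likely consequence. Post-assignment removal from the study, standard MANOVA, and silence on analysis set, removed families' data and missing data together lead to a complete-case comparison unless something is added.

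Its size cannot be fixed from the documents. Under a common correlation of 0.2-0.4, 20% v 10% loss moves the arm difference by 0.03-0.06 SD, or 6-12% of the margin. At the margin, false equivalence is then 8-12% or 2-3%, depending on which program loses more. If the correlation differs by arm within that range, the shift runs from about 0.01 SD in the opposite direction to 0.10 SD, and false equivalence reaches about 20%. Equal 20% loss can still give 13.5% or 1.4%.

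These figures assume TOST at 5%, which the plan does not name, normal scores and unchanged variance among those who remain. The change should be made. Confidence in material harm is medium at most.

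**What to change.** **Protocol.** Leave the clinical criteria for ending treatment unchanged, but separate ending treatment from ending follow-up. Keep all data already collected. State that missing one evaluation does not end follow-up. Seek T2 and T3 data from removed families where consent, legal authority for the child and the investigators' judgement of safety allow.

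**Analysis.**
- Analyse all randomised families in their assigned arm using all available T1-T3 data, by a likelihood-based mixed model, or by multiple imputation if MANOVA is kept.
- Report a per-protocol analysis alongside, because non-adherence can pull the arms together in an equivalence trial.
- State whether equivalence must hold on all the outcomes for which it is claimed or on any of them. Only the latter needs a multiplicity adjustment, for example Holm.
- Add an arm-specific missing-not-at-random sensitivity analysis, for example shifting missing T3 CBCL scores by 0 to 5 points separately in each arm.

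**Limits.** Few custody-loss families will be recovered, since legal status is an eligibility condition (Section 5), and no outright refusers. Loss that depends on T3 itself is only partly corrected, which is why the sensitivity analysis is needed.

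**Cost.** Protocol wording, ethics review of the changed removal wording, and some analysis work. At the assumed 20% v 10% loss, 150 × 0.20 + 150 × 0.10 = 45 families. At most 90 assessments at about $35 each ($30 card plus a book of about $5) come to $3,150. Staff time, tracing, any safety arrangements and video coding are extra and are not priced here. These assessments are already scheduled.

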Using a randomized experimental design, 300 parents of 2-5 year old children (predominantly African American and economically disadvantaged) referred for behavior problems to the Family Center at Kennedy-Krieger Institute will be randomized to Parent-Child Interaction Therapy (PCIT; n=150) or Chicago Parent Program (CPP; n=150). Data on child behavior problems, parent discipline strategies, parenting self-efficacy, observed parent behavior, parent stress, and depression will be obtained from all participants at baseline and post-intervention assessments. Social risk will be assessed at intake. Parent satisfaction, attendance, and engagement in the intervention will be obtained at post-intervention. Clinical costs related to PT and non-PT treatment will be measured monthly. This innovative study will be the first to compare the effectiveness, cost, and social validity of a brief treatment designed with and for ethnic minority parents of young children against a well-established treatment considered to be the "gold standard." Determining whether a PT treatment can yield comparable effects for low-income, racial/ethnic minority parents of young children but at less cost, in less time, and with greater social validity is of significant public health importance.

2. Objectives: To compare the:

1. Effectiveness of PCIT and CPP for reducing behavior problems in a predominantly African American sample of children 2-5 years old from low-income communities. It is hypothesized that CPP will be equally as effective as PCIT for reducing child behavior problems based on parent report and observation.
2. Effectiveness of PCIT and CPP for improving parenting behavior and self-efficacy among a predominantly African American sample of parents of 2-5 year old children from low-income communities. It is hypothesized that CPP will be equally as effective as PCIT for improving parent discipline, self-efficacy, and observed parenting behavior.
3. Perceived social validity of PCIT and CPP based on parent satisfaction scores, treatment attendance, and parent engagement ratings (i.e., active parent participation in the intervention

Date: January 30, 2012
Principal Investigator: [name]
Application Number: NA_00039328

sessions). It is hypothesized that parents in the CPP condition will (a) attend a higher percent of PT sessions, (b) be more engaged, and (c) report higher satisfaction than parents in PCIT.

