Exclusion criteria are parent(s) who (a) has (have) severe mental illness that would interfere with their ability to participate in PT (measured by the Psychosis Subscale of the Basic-24 or diagnostic intake clinician assessment) and/or (b) is (are) actively using drugs or alcohol, based on clinician assessment at intake. Foster parents or relatives without legal status for the child are excluded since they may not be able to complete the study.. Children who are actively suicidal, psychotic, or who have significant developmental delay (i.e., fail developmental screening using Ages and Stages Questionnaire at intake), congenital, genetic, or sensory abnormalities that interfere with the child’s understanding, cooperation, and/or participation in PCIT or CPP will be excluded and referred for appropriate treatment services or hospitalization. Children diagnosed with autism or Pervasive Developmental Disorder will also be excluded since there is no evidence that CPP or PCIT is effective with these populations.

6. Drugs/ Substances/ Devices

- a. NA
- b. NA.
- c. NA

7. Study Statistics

- a. Primary outcome variables: Child behavior problems (parent report and observed from video recorded parent-child play/clean-up), parenting self-efficacy, parent discipline, parent behavior (observed from video recorded play/clean-up), parent satisfaction, parent engagement in the intervention, parent attendance in PT sessions.
- b. Secondary outcome variables: cost variables are those related to (1) time required to administer PT (including lost time for missed appointments) and additional non-PT therapy services used by parent or child (i.e., individual therapy, medications); (2) therapist time, (3) parent time, (4) childcare provided during CPP sessions; (5) space (including one-way mirror).
- c. Sample Size and Statistical Plan: Sample size in this equivalence study is designed to determine whether CPP is as effective as PCIT for the targeted clinical population (i.e., outcomes do not differ clinically or statistically). We used CBCL scores (child behavior problems) to estimate the sample size positing the null hypothesis that the absolute difference in the post intervention means between the CPP and PCIT groups will be > 0.5 standard deviations (i.e., > 5 point difference on the CBCL). The alternative hypothesis is that the absolute difference in the two means is less than or equal to 0.5

Date: January 30, 2012
Principal Investigator: [name]

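### Eight unranked primary domains mix equivalence and superiority claims with no rule for which result decides the trial, and MANOVA does not supply the multiplicity control the plan credits it with

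*Combined protocol and SAP*

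**What the plan says.** Section 7a gives the primary outcomes as one list. It opens with "Primary outcome variables: Child behavior problems (parent report and observed from video recorded parent-child play/clean-up), parenting self-efficacy, parent discipline" and continues with "parent behavior (observed from video recorded play/clean-up), parent satisfaction, parent engagement in the intervention, parent attendance in PT sessions". Counting parent-reported and observed child behaviour separately, that makes eight domains in no stated order.

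Section 2 attaches a claim to each:

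- Objective 1, equivalence on two domains: "It is hypothesized that CPP will be equally as effective as PCIT for reducing child behavior problems based on parent report and observation".
- Objective 2, equivalence on three domains: "It is hypothesized that CPP will be equally as effective as PCIT for improving parent discipline, self-efficacy, and observed parenting behavior".
- Objective 3, superiority of CPP on three domains: "It is hypothesized that parents in the CPP condition will (a) attend a higher percent of PT sessions, (b) be more engaged", with higher satisfaction as part (c).

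Section 7c says "We used CBCL scores (child behavior problems) to estimate the sample size" and sets an equivalence margin of 0.5 SD, or 5 CBCL points. No other outcome has its own margin or sample-size calculation. On error control the section states "All baseline difference analyses and hypothesis testing will be conducted using 2-tailed tests and alpha =.05", with .01 for baseline comparisons only. It prefers repeated-measures MANOVA on the ground that "MANOVA corrects for multiple tests of hypotheses". Univariate ANOVAs follow a significant MANOVA, and no adjusted level is given for them.

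Table 1 in section 4b lists two CBCL scales (Externalizing and Internalizing), each measured at baseline, 4 months (T2) and 9 months (T3). Engagement and satisfaction are measured once, at T2 for CPP and T3 for PCIT. Attendance is recorded session by session during treatment. The 4 to 12 satisfaction items are to be analysed one by one.

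**The concern.** With eight co-listed primary outcomes and two kinds of claim, the plan needs a rule saying which results, and how many, make the trial a success. It has none. Even within the CBCL, the text chooses neither between the two scales nor between 4 and 9 months. A mixed set of results (equivalent on some domains, different on others) would leave the headline to judgement after the data are seen.

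The one safeguard offered is MANOVA. If it does not do what the plan says, the error rate for the primary claims is not what a reader would take it to be. The plan accepts the principle elsewhere: it tightens baseline comparisons to .01 because there are many of them.

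**Working it through.** **Inputs.** 150 per arm, margin 0.5 SD, alpha .05 two-sided (section 7c). Eight domains, five equivalence and three superiority (sections 7a and 2). Correlations between outcomes are not given, so values from 0 to 0.7 are assumed. No dropout is assumed.

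**1. The plan's own figure.** The standard error of the difference in SD units is √(2/150) = 0.1155, and 0.5/0.1155 = 4.330.

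- Two-sided test of a 0.5 SD difference: Φ(4.330 − 1.960) = 99.1%, which reproduces the stated 99%.
- Equivalence by two one-sided tests, true difference zero: 2Φ(4.330 − 1.645) − 1 = 99.3% at .05 each, and 2Φ(4.330 − 1.960) − 1 = 98.2% at .025 each.

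The sizing is therefore adequate for one CBCL equivalence claim.

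**2. Does MANOVA correct for this set?**

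- *Equivalence claims (five domains).* MANOVA's null hypothesis is no difference. A non-significant result does not show equivalence, and a significant one is not the gate an equivalence claim needs. It controls no error for these claims.
- *Superiority claims (three domains).* None has a baseline value, and two are measured at different times in the two arms. They do not fit a repeated-measures MANOVA. A separate one-occasion MANOVA is possible but not specified.
- *Follow-up ANOVAs.* These are unadjusted, so the gate protects fully only when no outcome truly differs.

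**3. Size for the three superiority outcomes.**

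- No gate, independent, any false difference in either direction: 1 − 0.95³ = 14.3%. At correlations of 0.7 to 0.3 it is about 11% to 14%.
- No gate, independent, false claim favouring CPP only: 1 − 0.975³ = 7.3%.
- MANOVA gate, no true difference (simulation, 200,000 draws): at most about 5%.
- MANOVA gate, one outcome truly different by 0.5 SD (same simulation): the chance of a false difference on another is about 8% to 10%.

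**4. Size for wider sets.**

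- Any one of eight may count as success, independent, no gate: 1 − 0.95⁸ = 33.7%.
- Any one of five equivalence domains may count, all truly at the margin, independent: 1 − 0.95⁵ = 22.6%.
- All five equivalence domains must pass: no inflation. If the five are independent with zero true differences and the 0.5 SD margin is applied to each, joint power is 0.993⁵ = 96% (tests at .05) or 0.982⁵ = 91% (tests at .025).

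**The case against.** The strongest defence has three parts.

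*Every domain has a prespecified claim, and CBCL is the natural lead.* This is true, and it limits the point. A reader might infer that the investigators could declare success on whatever they liked afterwards. The documents do not support that: section 2 fixes the direction of each claim, and only CBCL has a sample size and a margin. What remains is that CBCL is never designated as decisive and its scale and time point are left open.

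*Objectives 1 and 2 can be read as requiring every listed domain to pass.* On that reading error is not inflated. A reader might take 33.7% as the trial's false-positive rate, but it assumes that any single result suffices, that outcomes are independent and that no gate applies. It also pools false equivalence, which reaches 5% only at the margin, with false superiority, which needs no true difference. The plan does not adopt the any-one rule. It does not adopt the all-must-pass rule either.

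*A MANOVA gate does control something.* For difference tests it does, so calling the superiority error wholly uncontrolled would go too far. Nor does the plan say that all outcomes enter a single MANOVA, so one per objective is conceivable. But the plan does not say which outcomes enter which MANOVA, the control is partial once one outcome truly differs, and none of it carries over to equivalence.

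**Conclusion.** The concern holds in this form: the deciding outcome and success rule are missing, and the stated reliance on MANOVA is mistaken for the equivalence claims and incomplete for the superiority claims. This goes beyond missing detail, because the plan asserts a correction that its method does not deliver.

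The firm figures concern the three superiority outcomes: 14.3% for any false difference and 7.3% for a false CPP advantage if untested by a gate and independent, or about 8% to 10% for a false difference behind a gate when one outcome truly differs by 0.5 SD. Positive correlation lowers the ungated figures. Testing satisfaction item by item adds tests. The 33.7% should be quoted only as a conditional worst case. The change should be made, but the trial's design and size do not depend on it.

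**What to change.** Before outcomes are analysed by arm, amend sections 7a and 7c as follows.

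1. Name CBCL as the single outcome that decides the equivalence claim, on one scale at one time point. Externalizing at T3 is an example: section 4b puts PCIT at usually 6 to 8 months and CPP at 3, so both have usually finished by 9 months. Test it against the stated margin by requiring the confidence interval for the difference to lie within ±0.5 SD, and fix the interval's level (90% or 95%) in advance. Power is 99.3% or 98.2% under the assumptions above.
2. Make the other seven domains secondary, with DPICS-observed child behaviour, coded blind, as the key supporting outcome.
3. Test attendance, engagement and one prespecified satisfaction summary with Holm at an overall two-sided .05 (ordered p-values against .0167, .025 and .05), in place of reliance on MANOVA.

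Data collection and sample size do not change. The costs are:

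- Seven domains lose primary status.
- The lead outcome is parent report, and parents are not blinded (section 4c).
- Section 5 admits children with externalizing or internalizing problems, so one scale may not represent every child.
- At T3, CPP ended about 9 − 3 = 6 months earlier but PCIT only about 1 to 3 months earlier, counting from baseline.
- Holm costs some power. At its strictest step (.0167), power for a 0.5 SD effect falls from 99.1% to 97.4%. For a 0.3 SD effect it falls from 73.8% to 58.1%. These are upper limits on the loss, because Holm's later steps are less strict.
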